One pharmacological, iNO, and one non-pharmacological, the OLA strategy that combines lung recruitment and stabilization with individually optimized positive end-expiratory pressure (PEEP), and the possible synergistic effects of both interventions on RV performance. Apart from specifically targeting the described pathophysiological mechanisms, the combination of an OLA strategy and iNO could be especially beneficial, as modifying the pulmonary state through OLA could theoretically enhance the effects of iNO by significantly increasing the gas exchange area and, thus, alveolar ventilation. We will also study a series of closely related physiological variables to better characterize the effects of both strategies and their combination. This can help establish a better indication for iNO in cardiac surgery patients and improve our understanding of mechanisms that are also present in patients with acute respiratory distress syndrome (ARDS), albeit on a different scale.

2. Hypothesis

Inhaled nitric oxide (iNO) administered at a dose of 20 to 40 ppm in the immediate postoperative period of cardiac surgery improves pulmonary vascular mechanics and right ventricular function and synergistically interacts with alveolar recruitment in patients presenting with postoperative atelectasis.

3. Aims

Primary aim

- To study the effects of inhaled iNO on pulmonary vascular mechanics, right ventricular function, and right ventricular-vascular coupling in patients in the immediate postoperative period of cardiac surgery.

Secondary aim

- To compare the effects of iNO with standard care and with a lung recruitment maneuver on pulmonary vascular mechanics, right ventricular function, and right ventricular-vascular coupling in patients in the immediate postoperative period of cardiac surgery.
- To study patterns of redistribution of pulmonary blood flow measured by Electrical Impedance Tomography (EIT) that predict a positive effect on vascular mechanics and right ventricular function

4. Patients

Inclusion Criteria

Patients undergoing cardiac surgery who meet the following criteria will be included in the study:

- Age > 18 years
- Under controlled mechanical ventilation in passive conditions
- Presence of postoperative lung collapse (confirmed by pulmonary echocardiography and Air test)
- Preoperative left ventricular ejection fraction (LVEF) $\geq 30\%$.

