- Absence of hypovolemia: absence of "kissing" ventricles and/or collapsibility index of the superior vena cava < 20%.
- Stable spontaneous heart rhythm
- Postoperative hemodynamic stability:
- Mean arterial pressure (MAP) ≥ 60 mmHg
- Central venous pressure (CVP) ≥ 10 mmHg

Versión 2: September 1, 2023

- Heart rate (HR) \leq 100 bpm without tachyarrhythmias
- Lactic acid \leq 3 mmol/L
- Single vasopressor treatment
- Norepinephrine dose \leq 0.2 $\mu\text{g}/\text{kg}/\text{min}$, without an increase \geq 15% in the last 30 minutes.
- Obtained informed consent

Exclusion Criteria

- Cor pulmonale or preoperative pulmonary vascular pathology
- Absence of pre-existing chronic respiratory pathology.
- Pre-induction arterial oxygen saturation (SpO₂) $<$ 97% by pulse oximetry
- Chronic pulmonary hypertension (mPAP $>$ 35 mmHg) related to advanced COPD r chronic thromboembolic disease.
- Tricuspid or pulmonary valve surgery.
- Intra or postoperative use of nitroprusside or nitroglycerin.
- Preoperative dependency on inotropic or vasoconstrictor drugs.
- Use of levosimendan. Patients receiving dobutamine may be included as long as the infusion is \leq 2 $\mu\text{g}/\text{kg}/\text{min}$.
- Contraindication for transesophageal echocardiography (See Appendix I) (11)
- Absence of lung collapse
- Pacemaker dependency

5. Methods

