6.2 Pulmonary Recruitment Maneuver

The recruitment maneuver can cause transient hemodynamic deterioration and, less frequently, barotrauma. Safety criteria have been established to interrupt the maneuver (see 5.3.2):

- Desaturation: SpO₂ \leq 89%
- Mean arterial pressure < 55 mmHg or decrease \geq 30% from baseline
- Arrhythmias (tachyarrhythmias >120 bpm or bradyarrhythmias < 50 bpm)
- If the patient requires a pacemaker, a heart rate of 70-90 bpm based on hemodynamic response.

Barotrauma is a much less frequent and highly unlikely complication in patients with healthy lungs (as included in this study) and with the proposed pressures and duration (very brief and at moderate pressures) in this study.

A section for recording adverse effects will be added to the Case Report Form (CRF) of the study (in Excel format).

7. Ethical Considerations

The intervention period is very short, and most procedures are applied routinely in the postoperative period. Special precautions will be taken to interfere as little as possible with normal postoperative times and management (an average of 4 to 6 hours until patients are fully awake and extubated). However, since patients are randomized to receive different interventions, a study insurance will be organized.

During the study period, patients will remain sedated, primarily due to the continuous effects of anesthesia and, secondly, because routine administration of short-acting hypnotics and opioids is given during these early postoperative hours to ensure gradual and incident-free awakening. In any circumstance of patient discomfort or inappropriate early awakening with agitation, pain, or fighting against the ventilator, additional sedation/analgesia will be provided as per standard clinical practice. This will ensure patient comfort and prevent additional stress.

All research procedures will strictly adhere to the principles of good clinical practice and ethical principles established in the Declaration of Helsinki and the Oviedo Convention on Human Rights and Biomedicine.

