7.7 Monitorin

- Given that only 2 centers (Madrid and Barcelona) are participating in the study, it is planned to have 2 monitors located in each of the respective centers/cities. The monitor cannot, under any circumstances, be part of the investigative team.
- The objectives of study monitoring will be to ensure that:
- The rights and integrity of the subjects are protected.
- Trial data is accurate, complete, and verifiable with source documents.
- The trial is conducted in compliance with the approved protocol, following GCP and current regulations.

Monitoring Plan:

- Given the characteristics of the study, a risk-focused monitoring approach will be implemented. The variables collected in the CRF will be reviewed with special emphasis on safety variables and adverse effects. Verification and validation of the collection of key variables will be performed.
- Three monitoring visits will be scheduled (2 during the study and one final closing visit) during which the following checks/verifications will be conducted:
 - Critical variables to be monitored:
 - Verification of the collection of:
 - I. Informed Consent Verification
 - II. Confirmation of eligibility criteria
 - III. Correct randomization and administration of study drug
 - IV. Verification that identified data as critical variables. Review of source documents
 - V. Review of safety assessments (AEs, SAEs)
 - **Specific verifications to be performed at each visit:**
 - a) Written informed consent was obtained before each subject's participation in the trial.
 - b) The investigator recruits only subjects who meet the selection criteria.
 - c) The approved protocol is being followed correctly.
 - d) The time and storage conditions of iNO are acceptable, and supplies are sufficient during the trial; it is only administered at the doses specified in the protocol.
 - e) Source documents and other trial records are accurate, complete, up-to-date, and properly archived.
 - f) Accuracy and integrity of data entered into the CRF with respect to source documents and other trial-related records.
 - g) All adverse events have been reported appropriately and within the timelines specified in GCPs, the protocol, the Ethics Committee (CEIm), and relevant legal requirements.
 - h) The investigator maintains essential documents (Investigator File).

Versión 2: September 1, 2023

- i) Reporting any protocol deviations and taking necessary actions to prevent recurrence of detected deviations.

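### An exclusion criterion is inverted: as written it bars patients without chronic respiratory disease, the opposite of the healthy-lung population described in Protocol section 6.2

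*Protocol*

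**What the plan says.** In Protocol section 4 (Patients), the second item under Exclusion Criteria reads "Absence of pre-existing chronic respiratory pathology". The item before it is "Cor pulmonale or preoperative pulmonary vascular pathology". Later items exclude a pre-induction SpO₂ below 97% and chronic pulmonary hypertension (mean pulmonary artery pressure above 35 mmHg) "related to advanced COPD r chronic thromboembolic disease". The same list also contains "Absence of lung collapse".

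Section 6.2, on the safety of the recruitment maneuver, calls barotrauma a "highly unlikely complication in patients with healthy lungs (as included in this study". It adds a second ground, that the pressures are moderate and applied only briefly.

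Section 7.7 names confirmation of eligibility among the critical variables. At each visit the monitor is to verify that "The investigator recruits only subjects who meet the selection criteria".

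**The concern.** An item in an exclusion list names a condition that keeps a patient out. Here that condition is having no chronic respiratory disease, so the written rule admits only patients who have it. Section 6.2 describes the enrolled patients as having healthy lungs.

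Two things are at stake. The first is the population: a site that follows the words enrols patients unlike those the protocol describes, and some of them would be randomised to a maneuver whose risk statement partly assumes healthy lungs. The second is the audit trail: a site that follows the evident intent enrols patients who each meet a written exclusion criterion, and monitors are told to check exactly that.

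**Working it through.** No arithmetic is needed to establish the contradiction. The check reads the item under its heading and compares it with the rest of the protocol.

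1. **Literal reading.** Exclude if chronic respiratory disease is absent. The eligible set then contains only patients with chronic respiratory disease. Under the neighbouring items they must also have a pre-induction SpO₂ of at least 97%, no cor pulmonale or pulmonary vascular disease, and no chronic pulmonary hypertension of the kind described.

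2. **Population stated in section 6.2.** Patients with healthy lungs. This set and the set in step 1 are essentially mutually exclusive.

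3. **Could the list follow a different convention?** One might suppose that items starting with an absence are conditions to be satisfied. The item "Absence of lung collapse" rules this out. The inclusion list requires "Presence of postoperative lung collapse (confirmed by pulmonary echocardiography and Air test", so the collapse item makes sense only if lacking collapse excludes the patient. The first item, "Cor pulmonale or preoperative pulmonary vascular pathology", also names an excluding condition directly. The respiratory item cannot be silently reversed while the collapse item is read as it stands.

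4. **Does anything else support a lung-disease population?** No. The hypothesis and rationale (sections 1 and 2) concern postoperative atelectasis and pulmonary vascular effects after bypass, not chronic lung disease. The saturation threshold and the cor pulmonale item point away from such a population.

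5. **Is the text current?** Yes. It is in the body of Version 2, is a complete statement, and is not from a change log or a redacted area.

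6. **Extent.** Section 5.8.1 plans 54 patients, 18 in each of three groups (3 × 18 = 54).
   - Eligibility applies to all 54. If every enrolled patient is free of chronic respiratory disease, 54 of 54 meet the written exclusion. This is an upper bound, and the count falls by one for each enrolled patient who has such disease.
   - The barotrauma statement concerns only the group given recruitment (section 5.7, iNO-RM): 18 of 54, or one third.

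**The case against.** The strongest reply is that this is an obvious slip. The inclusion list uses the same kind of phrase correctly when it requires hypovolemia to be absent, so an inclusion-style line has probably landed in the wrong list. The neighbouring items make the intent largely recoverable, and enrolment of the wrong population is unlikely in practice. That is fair, and it limits the probable clinical harm. It does not make the text right: eligibility is audited against the written words, and reading the item sensibly is what produces the formal deviations.

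Section 6.2 also rests low barotrauma risk on brief, moderate pressures, which do not depend on lung history, and the maneuver has its own stability conditions and interruption limits. This stands. The literal rule takes away one of two stated grounds, not the whole safety argument, and only for the recruitment arm.

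That the two centres might read the item differently is a possibility only. Nothing in the protocol shows that they do.

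Finally, the separate item on pulmonary hypertension related to advanced COPD could suggest that milder lung disease was meant to be admissible, since a complete exclusion of chronic respiratory disease would make the COPD part redundant. Even so, patients with no lung disease would not be excluded, so the quoted line is still wrong. The overlap should be tidied in the same amendment.

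**Conclusion.** The concern holds. Section 4 contains an exclusion criterion whose literal meaning is the reverse of the population stated in section 6.2, and no other part of the protocol corrects it. It must be fixed, because it is an operative rule checked as a critical monitoring item.

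The formal eligibility problem reaches up to 54 of 54 patients, assuming that sites follow the evident intent and enrol only patients without chronic respiratory disease. The weakened risk statement concerns the 18 patients planned for the recruitment arm, and matters only if sites follow the words. Endpoints and sample size are not affected. That the line is a slip and not a deliberate choice is an inference from section 6.2 and the neighbouring criteria, which the sponsor should confirm.

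**What to change.** Amend the item in section 4 so that the presence of pre-existing chronic respiratory disease is the excluding condition, or move the present wording to the inclusion list. Either change brings it into line with section 6.2. In the same amendment, state how the corrected item relates to the one on COPD-related pulmonary hypertension, so that it is clear whether any chronic respiratory disease excludes.

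Update the eligibility check in the case report form and issue the corrected criterion to both centres and their monitors. If patients have already been enrolled, record which reading was applied to each.

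The cost is a one-line protocol amendment and a checklist update, with no change to sample size.

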5.1 Study Design

This is a prospective controlled and randomized physiological study that will be conducted at two hospitals. The intervention period will be limited to the first 2-3 postoperative hours. With a total of 54 patients, the study recruitment period is expected to last for 18 months.

Study Registration: EudraCT number 2022-003884-37

5.2 Follow-up and Study Variables

The main study variables will be right ventricular function parameters measured through transesophageal echocardiography (TEE), specifically those directly related to the estimation of right ventricular-vascular coupling (as described below). Additionally, variables derived from Electrical Impedance Tomography (EIT) will be recorded: regional distribution of ventilation and perfusion, and EIT pulsatility (12) (see below). Additional variables related to pulmonary vascular mechanics will be included in patients monitored with a pulmonary artery catheter.

5.2.1 Conventional Monitoring

Patients will receive routine postoperative monitoring, including invasive blood pressure measurement, surface electrocardiogram, SpO₂, and central venous pressure (CVP).

Mechanical ventilation will be provided by a Servo-U ventilator (Getinge, Solna, Sweden). This ventilator allows for the recording of all respiratory parameters, pulmonary mechanics, and ventilatory waveforms (Pressure, flow, and volume - time).

5.2.2 Echocardiography

At specified time points in the protocol, a specialist will perform transesophageal echocardiography (TEE) to assess right ventricular function and pulmonary circulation following the latest recommendations from the American and European Societies of Echocardiography (13). The following echocardiographic parameters will be studied:

Parameters of Right Ventricular Function

- Right ventricular end-diastolic and left ventricular end-diastolic diameters ratio
- Eccentricity index
- Right ventricular fractional shortening
- Tricuspid annular plane systolic excursion (TAPSE)
- S wave (Systolic Tissue Velocity)
- Myocardial Performance Index (MPI)
- Right ventricular ejection efficiency (RVEe) (14)
- TAPSE normalized to afterload (TAPSE/PAPs)
- Global longitudinal strain (speckle tracking)

Parameters of Afterload

- Estimated systolic pulmonary arterial pressure (PAPs)
- Estimated pulmonary vascular resistance using Doppler
- Notching pattern in the right ventricular outflow tract
- Right ventricular outflow tract acceleration time (RVOT-AT)
- Pulmonary pulse transit time (pPTT) (15)

From these right ventricular function variables, we have selected the primary variables (used for sample size estimation) that best inform about right ventricular-vascular coupling (16): RVEe; TAPSE/PAPs; pPTT, and contractility indicators: S' and TAPSE.

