5.8.2 Statistical Methods

Variables will undergo descriptive analysis of central tendency measures including mean, median, dispersion, standard deviation, and interquartile range, respectively. Homoscedasticity and normality assumptions will be confirmed using Levene's and Shapiro-Wilk tests, respectively.

Variables with normal distribution and similar variance will be compared using the t-test, and variables with non-normal distribution using the non-parametric Wilcoxon test. Pearson's chi-squared test will be used for categorical variables to compare groups at the three measurement points in the study, and Fisher's exact test when expected frequencies are < 5 .

For the comparison of more than two means with homoscedastic variances and normal distribution, ANOVA with post hoc testing will be conducted. For variables with heteroscedastic variances and/or non-normal distribution, the Kruskal-Wallis post hoc test will be applied. To analyze temporal evolution, a repeated measures ANOVA will be used with the intervention type as the main factor. In case of non-normality, the non-parametric Friedman test will be applied. Statistical significance will be set at $p \leq 0.05$. Statistical analysis will be performed using Stata v.15.

6. Safety and Adverse Events

To ensure safety during the 2-hour duration of the research protocol, the following precautions will be taken:

The inclusion of unstable patients or those who have had significant intraoperative complications leading to instability will be avoided.

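### Five unranked primary variables share one p ≤ 0.05 with no success rule; if any one may count, the false-positive rate is about 9–19% at assumed correlations of 0.95 to 0.5 (7–13% if only three are primary).

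*Protocol*

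**What the plan says.** Protocol section 5.2.2 (Echocardiography) goes through a long list of right ventricular and afterload measures and then states: "we have selected the primary variables (used for sample size estimation"). The selection is "RVEe; TAPSE/PAPs; pPTT, and contractility indicators", the last two being S' and TAPSE. That makes five variables, with no order of importance among them.

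Section 5.2 describes the main study variables as right ventricular function parameters, "specifically those directly related to the estimation of right ventricular-vascular coupling". On a narrow reading this covers only RVEe, TAPSE/PAPs and pPTT, because section 5.2.2 labels S' and TAPSE as contractility indicators. Five is the natural reading of 5.2.2; three is possible.

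Section 5.8.2 gives one threshold for everything: "Statistical significance will be set at" p ≤ 0.05. For more than two means with normal data and equal variances, "ANOVA with post hoc testing will be conducted"; the post hoc procedure is not named. Section 5.8.1 uses a single 95% confidence level and 54 patients, 18 per group. The protocol contains no hierarchy, no division of the significance level across variables and no rule for when the primary objective is met.

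**The concern.** With several primary variables of equal standing and the full 0.05 available to each, the probability of at least one significant result under no effect exceeds 0.05. Post hoc testing after ANOVA controls comparisons between arms within one variable. It does nothing across variables.

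If the trial reports a significant result on one of the five as its primary result, a reader cannot tell whether that variable was the one intended or the one that happened to succeed. The study is small and physiological, so what is at stake is a wrongly reported physiological effect of iNO.

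**Working it through.** **Inputs from the protocol.** Number of primary variables k = 5 (section 5.2.2), or 3 on the narrow reading of section 5.2. Threshold 0.05 (section 5.8.2). Three groups of 18 (section 5.8.1), and 3 × 18 = 54 as stated. The calculation behind the 54 cannot be reproduced, because no variable, SD or power is attached to it; that is a separate point.

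**Assumptions.** Two-sided tests (sidedness is not stated); normal data; one test per variable; the same correlation ρ between every pair. The protocol gives no correlations, so a range is shown. The repeated-measures analysis over T1 to T3 is not modelled.

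**Benchmark.** With one named primary variable, simulation gives 4.9–5.1%, the planned 5%.

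**Zero correlation.** P(at least one) = 1 − (1 − 0.05)^k. For k = 5: 1 − 0.95⁵ = 0.226. For k = 3: 1 − 0.95³ = 0.143. These are upper bounds under positive correlation.

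**Correlated variables.** For equicorrelated two-sided tests with c = 1.96:

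P(at least one) = 1 − ∫ φ(u) [Φ((c − √ρ·u)/√(1 − ρ)) − Φ((−c − √ρ·u)/√(1 − ρ))]^k du.

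The integral for k = 5 was compared with 100,000 simulated null trials per setting (3 × 18, omnibus ANOVA for each variable):

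| ρ (assumed) | Any of 5, integral | Any of 5, ANOVA | Any of 3, ANOVA | All 5, ANOVA | Holm over 5 |
|---|---|---|---|---|---|
| 0 | 22.6% | 22.6% | 14.3% | 0.0% | 4.9% |
| 0.3 | 20.9% | 21.0% | 13.8% | 0.0% | 4.7% |
| 0.5 | 18.3% | 18.9% | 12.6% | 0.1% | 4.3% |
| 0.7 | 14.8% | 15.3% | 11.1% | 0.3% | 3.6% |
| 0.9 | 10.2% | 10.6% | 8.6% | 1.5% | 2.5% |
| 0.95 | 8.5% | 8.8% | 7.4% | 2.3% | 2.0% |

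A single fixed between-arm t-test per variable gives almost the same any-of-five rates: 22.6% at ρ = 0, 18.5% at 0.5 and 8.7% at 0.95. An unequal assumed pattern (TAPSE with TAPSE/PAPs 0.8, TAPSE with S' 0.7, all other pairs 0.4) gives about 18%.

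Relative to 5%, the any-of-five rate is 8.8/5 ≈ 1.8 times at ρ = 0.95 and 18.9/5 ≈ 3.8 times at ρ = 0.5.

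**Power under Holm.** The first Holm step tests the smallest p-value at 0.05/5 = 0.01. For a two-group t-test with 18 per arm, a standardised difference of 0.961 gives 80% power at 0.05 and 56.6% at 0.01. Starting from an assumed 70% (difference 0.852) the figure is 44.3%; from an assumed 90% (difference 1.112) it is 72.5%. These are illustrations only, because the protocol states no power.

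**The case against.** The strongest objection is that the any-one rule is not written. The hypothesis and the primary aim join their domains with "and" rather than "or", and requiring all five variables would put the error rate at about 2% or less. This stands as a limit: the inflated rates are conditional. It does not remove the point, because the joining word links broad domains and sets no rule for the five variables. The all-five rule is no more written than the any-one rule.

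A second objection is that success rules and multiplicity control are often left to the SAP, which is not shown. That is fair for the detail of an adjustment. But naming the primary variable is a protocol decision, and this protocol has made it: several variables are called primary and one undivided threshold applies.

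A reader might infer a true error rate of 23%. That needs zero correlation between every pair, which is unlikely because TAPSE is the numerator of TAPSE/PAPs. On the three-variable reading TAPSE itself drops out, but measures chosen to reflect the same coupling are also unlikely to be uncorrelated.

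A reader might also infer further inflation from unadjusted t-tests across the three arm pairs, since section 5.8.2 says: "Variables with normal distribution and similar variance will be compared using the t-test". The same section assigns comparisons of more than two means to ANOVA with post hoc testing or to Kruskal-Wallis, so the text does not support that inference.

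**Conclusion.** The point holds in conditional form. The protocol fixes several co-listed primary variables at an undivided 0.05, with no control across them and no success rule. If any one suffices, the false-positive rate is above 5% on either count of variables and at every correlation examined: about 9–19% for five and 7–13% for three at correlations of 0.95 to 0.5, bounded by 23% and 14%. If all five must succeed, false positives are not the problem and the cost falls on power.

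The size rests on assumed, equal correlations and on one test per variable. This is something the sponsor should correct; in a physiological study of 54 patients the consequence is limited. The wording of the aims and the 15% improvement that is tied to no variable are separate points, and this conclusion does not depend on them.

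**What to change.** Preferred: before any comparative data are seen, name one primary variable (for example one of the coupling measures, in line with section 5.2), one time point (for example T3) and one between-arm contrast, tested at two-sided 0.05. Make the other variables secondary. This restores the 5% rate, changes wording in sections 5.2.2 and 5.8.2, and loses no data. The price is that the other four variables become supportive. Whether 54 patients suffice for the chosen variable would still have to be shown.

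Alternative: keep all five as primary under Holm, which holds the chance of any false positive to at most 5% (2–5% in the table), provided each variable contributes one prespecified, valid p-value. The protocol should then state that the first step is at 0.01 and what that does to power; an assumed 80% would become about 57% at that step.

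If all five are meant to be required, the protocol should say so and justify the power for that joint requirement.
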